Comparison of 1,550-nm fractional and 755-nm alexandrite picosecond laser for the treatment of acne scarring

BACKGROUND:

Acne is a highly prevalent disease and post-acne scarring has shown to have detrimental effects on a person's physical, mental, and social well-being (Purvis et al. 2006). Acne scars can be divided in general categories of hypertrophic or keloid scars, atrophic scars (icepick, rolling, Boxcar), and pigmentation alterations (redness, hypo and hyper-pigmentation). This study will focus on treatment of moderate to severe grades of atrophic acne scarring.

Both lasers in this study in this study are already FDA approved treatment modalities for acne scarring.

History 1550nm Erbium laser:

Fractional lasers are effective in treating dermatological diseases that require large treatment areas and high pulse energy, and well tolerated by patients. A non-ablative 1550-nm erbium-doped fractional photothermolysis system is widely used for clinical purposes (Cho et al. 2010). As the stratum corneum remains intact after FPS treatment and epidermal barrier function is therefore preserved, side effects and recovery time are markedly reduced, as compared to ablative lasers.

Fractionated photothermolysis invented in 2001 produces microscopic treatment zones (MTZ) of full thickness thermal damage by a mid-infrared laser. MTZs sit among the surrounding viable skin while keeping the stratum corneum intact. Each MTZ inside the skin undergoes local epidermal necrosis and collagen denaturation. Within 24 hours, the reepithelization occurs, followed by epidermal regeneration.

In 2008, Chrastil et al. investigated the efficacy and safety of second-generation 1,550-nm FPS in treatment of acne scarring (Chrastil et al. 2008). The majority of patients achieved a 50% to 75% improvement in facial and back acne scarring (18 of 29 patients). Side effects were minimal and no posttreatment pigmentary changes were noted, including within patients with Fitzpatrick Skin Types III to V. In 2009 HU et al. also investigated the effect of 1550-nm non-ablative FPS on atrophic scars, specifically within Asian patient with Fitzpatrick skin type III-IV. Good to excellent improvement was noted in 60% of the patients after 1 month, with unremarkable side effects (Hu et al. 2009).

To this date the efficacy and safety of 1,550-nm fractionated photothermolysis system has not been compared to other non-ablative lasers (Abdel Hay et al. 2016).

History 755nm picosecond laser:

A recent study investigated the safety and efficacy of a 755-nm alexandrite picosecond pulse duration laser with diffractive lens array for the treatment of facial acne scarring (Brauer et al. 2015). This laser has also been FDA approved for treatment of atrophic acne scars. The evolution from nanosecond to picosecond lasers can deliver more targeted energy, and with lower fluence, leading to fewer adverse effects. An innovative optical attachment, a diffractive lens array, has been developed that augments distribution of energy to the treatment area. This method has a greater pattern density per pulse, and was shown in this study to improve appearance of acne scars.

In the Brauer study, patients received 6 treatments with a 755-nm picosecond laser with a spot size of 6 mm, fluence of 0.71 J/cm², repetition rate of 5 Hz, and pulse width of 750 picoseconds in combination with a diffractive lens array, allowing for greater surface area and pattern density per pulse. This treatment produced improvement in appearance and texture at 3 months after the last treatment, with objective findings similar to those published for a series of fractional ablative laser

treatments. The study demonstrated high patient satisfaction and no significant lasting side effects among Fitzpatrick skin types I through V.

Introduction:

We will compare these two lasers in the treatment of acne scarring by performing a split faced randomized trial with three treatments over 3 months. Photographs will be taken prior to treatment and after final follow up with photographic review by blinded reviewer.

Hypotheses for this study:

1- There is no significant difference in efficacy of acne scar treatment with fractionated 1550-nm laser and 755-nm picosecond laser in combination with a diffractive lens array.

2- The 755-nm picosecond laser in combination with a diffractive lens array has superior side effect profile as compared to fractionated 1550-nm laser in treating acne scars.

PURPOSE & OBJECTIVES

Objective: To compare efficacy and safety of fractionated 1550-nm laser and 755-nm alexandrite picosecond laser in combination with a diffractive lens array, in treatment of moderate to severe acne scars.

Primary Endpoint: Improvement in acne scarring measured by photographic review. Measured by blind reviewer and quantitative 3D imaging.

Exploratory Objective: Comparing side effects of the different lasers.

Exploratory Endpoint: measure side effects by patient reported adverse events.

PARTICIPANT ELIGIBILITY

INCLUSION CRITERIA

Men and women with Fitzpatrick skin types I through V and facial acne scarring of grades III-IV (moderate to severe), who are able to give consent, will be enrolled. Both sides of the participants' face should have similar amount and severity of acne scarring. Participants will be over 18 years old. Patients have to be otherwise healthy without a history of skin cancer, keloidal scarring, localized or active infection, immunodeficiency disorders, and light sensitivity.

EXCLUSION CRITERIA

Patients have to be overall healthy without a history of skin cancer, keloidal scarring, localized or active infection, immunodeficiency disorders, and light sensitivity. Per PI discretion, any serious medical condition that may interfere with the study. In addition, patients who have been taking isotretinoin for a period of 6 months before treatment will be excluded.

JUSTIFICATION REQUIREMENTS FOR INCLUSION OF VULNERABLE POPULATIONS

Pregnant women are not excluded from this study and we will not perform pregnancy tests during the study. Neither laser device used in this study has shown risks during pregnancy or to the fetus.

Acyclovir is the only systemic medication used in this study to prevent herpetic outbreaks after laser treatments. Acyclovir is category B in pregnancy.

CDC studies have indicated that "Based on comparisons with birth defects surveillance data maintained by CDC, the registry findings summarized in this report indicate no increased risk for birth defects among infants born to women exposed to acyclovir during pregnancy". Source is the CDC website at:

<https://www.cdc.gov/mmwr/preview/mmwrhtml/00022071.htm>

Recruitment:

Patients recruited will all be current patients of U of U dermatology department. We will send out an email to all current dermatologists within the department asking for referrals to this study. If they have patients with acne scarring who are interested in participating in this study, they will refer the patients to the study by providing the PI and sub-investigator with patient's name and university ID number. There will also be a flyer about the study available in the dermatology clinics of the U of U. The patient's medical record will then be reviewed by the PI or sub-investigator in order to determine if patient meets inclusion criteria. A recruitment letter (see documents sections), will then be mailed to the potential participants signed by the PI. The letter will give a brief description of the study, and contact information for opting out or asking for more information. Letter will let possible participants know that they will be called by the PI or sub-investigator to invite them to an introductory visit during which they will be given details about the study and their eligibility will be determined by the PI. If the patients are interested in participating in the study at this visit, they will be asked to sign the consent form (see documents section).

STUDY PROCEDURES

Screening visit- this visit takes place anytime between one week to 6 months prior to initiation of treatments at week zero. Participants will be screened based on inclusion and exclusion criteria, Fitzpatrick skin type will be determined, and full details of study are explained. If participation is desired, patients will sign the consent form at this time. Prescription may be given for oral acyclovir and topical triamcinolone.

Treatment phase

Week 0:

- Baseline full face photographs taken
- Laser treatment #1 to both sides of the face (R and L sides of the face are each treated with one of the two study lasers based on randomization)
- Review post-laser standard-of-care skin care with participants (sun avoidance, sunscreen use, moisturizer use)
- Complete VAS pain assessment (see documents attached)
- Prescription given for oral acyclovir and topical triamcinolone per protocol

Week 4:

- Full face photographs taken
- Review and evaluation of any adverse events from previous session and complete assessment of adverse events form (see attached documents)
- Laser treatment #2 to both sides of the face (R and L sides of the face are each treated with one of the two study lasers based on randomization)
- Review post-laser standard-of-care skin care with participants (sun avoidance, sunscreen use, moisturizer use)
- Complete VAS pain assessment (see documents attached)
- Prescription given for oral acyclovir and topical triamcinolone per protocol

Week 8:

- Full face photographs taken

- Review and evaluation of any adverse events from previous session and complete assessment of adverse events form (see attached documents)
- Laser treatment #3 to both sides of the face (R and L sides of the face are each treated with one of the two study lasers based on randomization)
- Review post-laser standard-of-care skin care with participants (sun avoidance, sunscreen use, moisturizer use)
- Complete VAS pain assessment (see documents attached)
- Prescription given for oral acyclovir and topical triamcinolone per protocol

Week 24:

- Full face photographs taken
- Review and evaluation of any adverse events or serious adverse events
- Complete physician assessment of improvement of acne scarring (see documents attached)
- Participants fill out final satisfaction survey (see documents attached)

STUDY TREATMENT

Both laser treatments are FDA approved for acne scarring and both are considered as part of standard of care of acne scarring. The procedures that are for research purposes only are:

- blinding the participant to which side of face receives which laser
- randomization of which side of face receives which laser
- review of clinical photos by blinded dermatologist

STATISTICAL CONSIDERATIONS

Analysis method will be based on the following table:

Outcome	When measured	Analysis Method
VAS pain score after each treatment	After each treatment	T test to compare means across laser type at each time point. Repeated measures mixed effects models to compare effects across study.
Equivalence across laser type.		One sided t test for non-inferiority or equivalence.
Proportion Satisfied or Extremely Satisfied	Final visit at 24 weeks (3 moths post final laser tx)	Verify that there is no stat. sig dif between laser types, Then using score of side with lowest satisfaction test if proportion is different from 0 or proposed placebo effect.
Mean of scores from 3 physician evaluators on improvement in texture and overall appearance	Week 24 photos (3 months post final treatment)	T test to compare means across laser type. Repeated measures mixed effects models to compare effects across all study timepoints.

All analyses will be conducted using SAS software version 9.4. All test will be two-sided with an alpha level of 0.05 with the exception of the non-inferiority analysis which will be a one-sided test with and alpha level of 0.025.

Power and Sample Size

Sample size estimation is based on the primary aim of patient-reported scar improvement. The goal of the study is to show non-inferiority of the two types of laser treatments. Cho (2009) found that the mean difference in patient satisfaction scores (scores ranged from 0 to 3) across the two laser treatments was -0.75 with a standard deviation of 0.71 Using this standard deviation of 0.71 to power for a non-equivalence test, it was found that a sample sizes of 8 achieves 80% power to detect non-inferiority using a one-sided t-test.

Results from PASS software:

	Non-Inferiority	Actual	Significance		Standard
Power	N	Margin	Difference	Level	Deviation
		(-NIM)	(D)	(Alpha)	Beta
					(S)
0.80388	18	-0.500	0.000	0.02500	0.19612
					0.710

If the goal is to establish non-inferiority of the new laser to the old, 18 subjects are needed. The assumption is that there is no difference in the two lasers, but the investigator is willing to accept a margin of inferiority of 0.5. Allowing for a 10% dropout rate, 20 subjects would need to be enrolled. The investigator would also like to establish that either laser type achieves a certain proportion of good or excellent results on subjective assessment. Assuming that the two methods are equivalent, we want to determine if the effect of either side would be better than a placebo effect or a much less effective treatment. The following table gives scenarios of detectable difference if 18 subjects complete the study for a two-sided test at alpha = 0.05.

With 18 subjects completing the study and a power of 0.80 the following differences between those rating either laser treatment as satisfied or very satisfied could be detected:

% satisfied/ext. satisfied if no effect (as compared to an ineffective or no treatment)	% satisfied/ext. satisfied if an effect	Detectable difference
0.0500	0.2339	0.1839
0.1000	0.3318	0.2318
0.1500	0.4126	0.2626
0.2000	0.4839	0.2839
0.2500	0.5487	0.2987
0.3000	0.6085	0.3085
0.3500	0.6640	0.3140
0.4000	0.7158	0.3158
0.4500	0.7641	0.3141
0.5000	0.8090	0.3090

STUDY DESIGN: This is a Prospective, Blinded, Split-faced, comparative study using a blinded assessor.

SAFETY MONITORING

Safety monitoring for this study will be performed by PI, [name]. Data and events that will be monitored include:

- Immediate side effects from laser treatments will be monitored and recorded, such as redness, edema, blistering, hyperpigmentation, pain.
- Risks of the both types of lasers used are similar and include redness, swelling, hyperpigmentation (temporary darkening of your skin), scarring, crusting, bacterial skin infection, cold sore reactivation, and blistering of the skin.

Participant Withdraw Criteria

Participants may withdraw at any time during the trial.

Study Modification or Stopping Criteria

The study could be stopped or modified if there are severe or irreversible unforeseeable side effects of the two laser treatments used.

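### The declared primary endpoint (photographic review and 3D imaging) is not the patient-reported outcome the trial is sized on, and no margin or non-inferiority test is tied to it

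*Combined protocol and SAP*

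**What the plan says.** **Objectives.** Purpose & Objectives states: "Primary Endpoint: Improvement in acne scarring measured by photographic review. Measured by blind reviewer and quantitative 3D imaging". The first hypothesis in the Introduction is worded as the absence of a significant difference in efficacy.

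**Sizing.** Power and Sample Size states: "Sample size estimation is based on the primary aim of patient-reported scar improvement". It continues: "The goal of the study is to show non-inferiority of the two types of laser treatments". The inputs are a 0–3 patient satisfaction score from a cited study, SD 0.71, margin 0.5 and a true difference of 0. The PASS row gives power 0.80388 at N = 18, and 20 are to be enrolled after 10% dropout.

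**Alpha.** Statistical Considerations sets two-sided 0.05 for all tests, "with the exception of the non-inferiority analysis which will be a one-sided test with and alpha level of 0.025".

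**Analysis table.**
- Photographic row: "Mean of scores from 3 physician evaluators on improvement in texture and overall appearance", from Week 24 photographs. Method: "T test to compare means across laser type. Repeated measures mixed effects models to compare effects across all study timepoints". No margin.
- Equivalence row: a one-sided t test for either non-inferiority or equivalence. No outcome, time point or margin appears in the text we have.
- Satisfaction row: a proportion at the final visit. The lasers are first checked for a significant difference; the lower side is then tested against zero or a placebo rate.
- 3D imaging: no row, and no visit in Study Procedures lists it.

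**The concern.** Two different outcomes, rated by different people, are each called primary, and the plan does not say which one decides the trial. The outcome with a margin and a power calculation (mean patient score) has no row of its own in the analysis table. The outcome declared primary (photographic review) has a row but no margin, no planning SD and no power.

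This matters because the stated goal is non-inferiority. A two-sided test that fails to reject does not show that one laser is not worse than the other by more than an acceptable amount. The plan's own wording invites that misreading: both the efficacy hypothesis and the satisfaction row rest on finding no significant difference. With no rule for choosing between the two outcomes, a favourable result on either could later be presented as the trial's answer.

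**Working it through.** **1. Reproduce the plan's figure.** Inputs from Power and Sample Size: margin 0.5, SD 0.71, true difference 0, one-sided alpha 0.025. The design is split-face, so the test is a paired (one-sample) t test.

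Power = 1 − F(t(0.975, n−1); df = n−1, ncp = (margin/SD) × √n), where F is the noncentral t distribution function.

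- margin/SD = 0.5/0.71 = 0.704. At n = 18, ncp = 0.704 × √18 = 2.988 and t(0.975, 17) = 2.110, so power = 0.80388. This matches the PASS row.
- n = 17 gives 0.778, so 18 is the smallest n reaching 80%.
- Enrolment: 18/0.90 = 20, as stated.

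The arithmetic is right. Its inputs belong to the patient score.

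**2. What 18 pairs give on the photographic score.** The documents give no scale, SD or margin for it, so only the ratio margin/SD of the paired difference can be used. Solving the formula for 80% at n = 18 gives a ratio of 0.701. The ratios below are assumptions that span both sides of it:

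| Assumed margin/SD | Power at 18 pairs | Completers for 80% | Enrolled (÷ 0.90) |
|---|---|---|---|
| 0.5 | 52% | 34 | 38 |
| 0.6 | 67% | 24 | 27 |
| 0.8 | 89% | 15 | 17 |
| 1.0 | 98% | 10 | 12 |

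**3. What a non-significant difference test would show.** Assume, for illustration, that the photographic paired SD is also 0.71. Using a two-sided 0.05 paired t test at n = 18:

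- True deficit 0.3: ncp = (0.3/0.71) × √18 = 1.793. The test is non-significant 60.6% of the time.
- True deficit 0.5: ncp = 2.988. It is non-significant 19.6% of the time.

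So a result of no significant difference is likely under a moderate true deficit, and occurs about one time in five when the deficit equals the 0.5 margin used for the patient score.

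**4. The open choice between non-inferiority and equivalence.** Take the patient score with limits ±0.5, SD 0.71, true difference 0, and two one-sided tests by numerical integration:

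- 0.025 per side: power 61% at n = 18; 24 completers for 80%.
- 0.05 per side: power 78% at n = 18; 19 completers for 80%.

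The alpha sentence covers the non-inferiority analysis and gives no per-side level for equivalence, so both are shown.

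**The case against.** **The equivalence row may cover the photographic score.** It names no outcome, so it could be meant for any row, and a cell may have been lost in reading the table from PDF. This stands in part. A reader might infer that the plan allows only tests of difference on its declared primary, and the documents do not support that. They support a narrower statement: no non-inferiority test is explicitly tied to the photographic score, and the only margin given belongs to the patient score. Even if the row was meant for photographs, that endpoint still has no margin or power.

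**The photographic endpoint may be well powered.** This stands. A reader might infer that the trial is underpowered on its declared primary. Ratios above about 0.70 give more than 80%, and nothing in the documents favours low ratios. The 95% confidence interval half-width at 18 pairs, 2.110/√18 = 0.497 SD, lies inside the patient score's standardised margin of 0.704. Power is unknown, not shown to be low.

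**Side points look worse than they are.** The prose says "a sample sizes of 8 achieves 80% power to detect non-inferiority using a one-sided t-test", and n = 8 would give 41% power. But the PASS row and the next paragraph ("If the goal is to establish non-inferiority of the new laser to the old, 18 subjects are needed") both say 18, and 20 enrolled follows from 18; this is a slip. The photographic row does not say that its evaluators are blinded, but the Introduction, Study Treatment and Study Design all describe blinded review, so unblinded rating cannot be inferred. Only the number of raters, one or three, is unreconciled. New and old laser are not defined, although the background suggests which is meant.

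**Details may be in the attached forms.** We cannot see them. A form could supply a scale, but it would not settle which endpoint is primary.

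**Conclusion.** The concern holds, as a mismatch between the declared primary endpoint and the outcome behind the sample size. It should be resolved before the analysis.

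Certain from the documents: two outcomes are called primary; 0.80388 at 18 pairs applies to the patient score; no margin exists for the photographic score; and no row names the mean satisfaction difference that was sized. 3D imaging has no visit or analysis in the text available.

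Conditional: every power figure for the photographic score rests on an assumed margin/SD, and the 61% and 20% non-significance rates on an assumed SD of 0.71. The equivalence figures matter only if that reading of the table is intended.

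The severity comes from the endpoint mismatch and the missing margin. The 8, the rater count and the undefined new and old lasers are minor and would not carry it alone.

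**What to change.** Before anyone sees any outcome by laser, name one primary endpoint in the same words in the objectives, the power section and the analysis table. Tie the one-sided 0.025 paired non-inferiority test at Week 24 to it. State the direction (which laser is new, which old) and a margin on that outcome's own scale. State that a non-significant difference test will not be read as non-inferiority.

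**Option A, photographic score primary.** Set and justify its margin. State that the 80.4% power applies to satisfaction only, and give the condition that margin/SD must be at least about 0.70. Reconcile one blinded reviewer with three evaluators. Cost: the power statement becomes conditional, and could be above or below 80% until a paired SD is available.

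**Option B, patient score primary.** Change the primary endpoint in Purpose & Objectives to match. Add the paired mean-difference test with margin 0.5 to the table, and confirm that the final survey is scored per side on the 0–3 scale behind that margin. The 18 completers and 20 enrolled stand. Cost: a patient rating becomes primary in place of blinded photographic review.

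Under either option, give 3D imaging a time point and an analysis or state its status, and correct the 8 to 18. The edits are wording in three sections and add no visits, unless the sponsor schedules 3D imaging or adds participants under Option A. Choosing non-inferiority gives up an equivalence claim, which on the patient score would need 19 or 24 completers, depending on the per-side level.

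### Apart from VAS pain, no side-effect comparison between the lasers is planned, and events after session 3 are first scheduled for review 16 weeks later with no form named

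*Combined protocol and SAP*

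**What the plan says.** **The claim.** The second hypothesis states "The 755-nm picosecond laser in combination with a diffractive lens array has superior side effect profile as compared to fractionated 1550-nm laser". Under Purpose & Objectives the comparison is labelled exploratory ("Exploratory Objective: Comparing side effects of the different lasers"), and the endpoint is to "measure side effects by patient reported adverse events".

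**Collection.** Under Study Procedures, the Week 4 and Week 8 lists each contain "Review and evaluation of any adverse events from previous session and complete assessment of adverse events form". Session 3 is given at Week 8. The next listed visit is Week 24, where the item is "Review and evaluation of any adverse events or serious adverse events". No form is attached to that item, although the same Week 24 list refers to attached documents for the physician assessment and the satisfaction survey.

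**Safety monitoring.** This section says that immediate effects, with redness, edema, blistering, hyperpigmentation and pain as examples, are monitored and recorded. It names no visit, form or side of face. It also lists eight risks common to both lasers.

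**Analysis.** The table under Statistical Considerations covers VAS pain after each treatment (t test by laser type plus a mixed model), equivalence, satisfaction and physician-rated improvement. It has no row for adverse events.

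**The concern.** A directional hypothesis has a named endpoint but no planned analysis of it. The summary, the unit (side, session or participant) and the test would all be chosen after the data are seen. The conclusion on side effects could then rest on pain alone, or on whichever effect happens to differ.

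The data for the three sessions are also not collected alike. Two sessions have a form at 4 weeks. The third has an unstructured review at 16 weeks. Swelling, crusting or blistering that appears after the treatment day and resolves within days or weeks may not be remembered, or not be attributed to the correct side, four months later. Under-recording of this kind cannot be repaired at the analysis stage.

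**Working it through.** **1. Timing.** From the visit lists:
- Session 1 (Week 0) to review (Week 4): 4 weeks, form named.
- Session 2 (Week 4) to review (Week 8): 4 weeks, form named.
- Session 3 (Week 8) to review (Week 24): 24 − 8 = 16 weeks, or 16 × 7 / 30.44 = 3.7 months, no form named.

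The recall period after session 3 is 16 / 4 = 4 times as long. The analysis table describes Week 24 as 3 months after the last treatment. Even 3 months, about 13 weeks, would be more than three times the earlier interval.

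**2. Share of the data affected.** With 18 completers and 3 sessions there are 54 sessions, of which 18 (one third) are third sessions.

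**3. The plan's own sample-size figure.** No figure is given for side effects, so 18 completers is the number to work with. It reproduces. A one-sided paired t test with margin 0.5, SD 0.71, alpha 0.025 and N = 18 has noncentrality 0.5 / 0.71 × √18 = 2.99 on 17 df. Power is 0.8039, against 0.80388 stated. Enrolment is 18 / 0.9 = 20, as stated.

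**4. What 18 pairs can show on a yes/no side effect.** Each participant is own control, so only participants with the event on one side only (discordant) carry information. The exact two-sided McNemar test is a sign test on these:
- 5 of 5 one way: 2 × 0.5⁵ = 0.0625, not significant.
- 6 of 6 one way: 2 × 0.5⁶ = 0.031, significant.
- With one participant the other way, 7 against 1 gives 2 × 9 / 256 = 0.070 and 8 against 1 gives 2 × 10 / 512 = 0.039, so 9 discordant participants are needed.

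**5. Power.** The number discordant is binomial (18, a + b), where a is the proportion with the event on the 1,550-nm side only and b the proportion with it on the 755-nm side only. Given that number, the split is binomial with probability a / (a + b). Summing over all outcomes significant in favour of the 755-nm laser at two-sided 0.05 gives the power below. The documents give no event rates, so a and b are assumptions.

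| a | b | Power |
|---|---|---|
| 20% | 0% | 13% |
| 30% | 0% | 47% |
| 40% | 0% | 79% |
| 30% | 5% | 26% |
| 40% | 5% | 51% |
| 50% | 5% | 72% |

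Power of 80% needs a of about 41% if b is 0, and about 55% if b is 5%.

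**The case against.** **Pain is compared by laser.** This stands. Safety monitoring counts pain as a side effect, and it is scored and compared by laser after every session, including the third. A reader might infer that no side effect at all is tested by side; the analysis table contradicts that. Pain scored after treatment does not, however, measure blistering, crusting or pigment change.

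**Immediate effects are recorded.** This stands in part. A reader might infer that a participant lost after Week 8 leaves no record of session 3. That is not so: VAS pain is scored at Week 8, and same-day effects may be recorded under safety monitoring. What is missing is a scheduled review of later events before Week 24.

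**The form may already record side.** The attached form is not among the documents reviewed. A reader might infer that events are not recorded by side; the text is silent, which is a reason to ask and not proof of a gap.

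**The objective is exploratory, and two of three sessions have structured data.** Both are true, and both lower the weight. Hypothesis 2 is under-specified, not unanswerable. The label does not explain why the named endpoint has no analysis.

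**Multiplicity.** A reader might infer a false-positive chance of about one third from testing all eight listed risks at 0.05 (1 − 0.95⁸ = 0.34). The documents plan no such tests, and the exact test at n = 18 is well below its nominal level: its true size is about 0.3% to 2.3% for null discordance of 20% to 60%. Eight independent tests would then give about 3% to 17%.

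**Low power undercuts an added test.** This is fair, and it is why the comparison should be labelled exploratory with its limits stated.

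**Conclusion.** The point holds as a should-fix. Apart from VAS pain, the endpoint named for hypothesis 2 has no planned comparison between lasers. One third of the sessions (18 of 54 in completers) has its only scheduled adverse-event review at 16 weeks instead of 4, with no form named. The timing and the missing row follow directly from the text. That delayed or short-lived events would be under-recorded is a judgement about recall, and its size cannot be calculated from the documents. The power figures rest on assumed discordance rates, but throughout the range shown only large differences between sides would be detected. The efficacy comparison and its sample size are not affected.

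**What to change.** 1. Collect session-3 events on the same adverse events form about 4 weeks after session 3, for example by phone, and complete the form again at Week 24. If the extra contact is not adopted, report session 3 separately because of its longer recall.
2. Confirm that the form records each event by side of face; add a side field if it does not.
3. Add one row to the analysis table: a single summary per participant and side over the sessions, compared within participant at two-sided 0.05 and labelled exploratory. Use exact McNemar for any event, or Wilcoxon signed-rank for worst severity. Choose one in advance. If mild redness is expected on nearly every side, few pairs would be discordant for any event, and worst severity would carry more information. Report individual effects descriptively.
4. State that 18 pairs can detect only large differences, with the minimum of 6 discordant participants all in one direction and the assumed-rate power figures.

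The cost is one short contact per participant (at most 20), an existing form at an existing visit, possibly a side field, and one added analysis. The treatment schedule and the sample size do not change. The value is greatest if this is done before data collection, since events that were not recorded cannot be recovered.
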